#### ***10.2. Statistical Methodology***

A summary of the data will be prepared for all measurement time points. Summaries of the changes observed between the 1 month and 3 month post-operative visits will also be summarized.

For variables measured on a continuous scale, these summaries will include the sample size, as well as the mean, standard deviation, median, minimum, and maximum. For variables measured on a categorical scale, summaries will provide the number and percentage of subjects who provided each score (or change in scores). These summaries will be provided for all eyes completing the study.

##### **10.2.1. Within-treatment Changes**

For variables measured on a continuous scale, the statistical significance of within-treatment changes between time points will be investigated using the TOST equivalence test.

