### 3. GENERAL INFORMATION

Objective	To evaluate refractive stability (spherical equivalent change $\leq$ 0.50D from 1-month to 3-months).  The hypothesis is that the Alcon Clareon® intraocular lens provides stable refractive stability evaluated over the postoperative 3 months with 80% of subjects achieving $\leq$ 0.50D spherical equivalent change from 1-month to 3-months.
Test Article(s)	Clareon® Intraocular lens
Control Article(s)	None.
Sample size	60 eyes of 30 subjects
Study Population	Subjects $\geq$ 50 years of age presenting for cataract surgery who are appropriate candidates for intraocular lens implantation.
Number of sites	One
Study Design	Prospective, non-randomized, single-arm study.
Masking	Evaluator masked
Variables	Primary: Refractive stability (spherical equivalent change $\leq$ 0.50D from 1-month to 3-months)  Secondary: 

• Binocular visual acuity outcomes (uncorrected and best-distance-corrected) at distance (4-6 m) and intermediate (80 cm) at 1 month and 3 months

• Percentage of patients cumulative distribution achieving 20/20 or better, 20/25 or better, 20/30 or better and 20/40 or better intermediate vision at 80 cm

• Binocular defocus curve at 3 months

Duration / Follow-up	Preoperative to 3 months postoperative

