## 7. SUBJECTS

### 7.1. Subject Population

Eligible test subjects will be presenting for cataract surgery and who are interested in and appropriate candidates for intraocular lens implantation.

A total of 60 eyes of 30 subjects at one site will be enrolled. Both eyes of a subject must be enrolled. Subjects must meet the inclusion criteria. Prior to enrollment, subjects will be provided information on the study and asked to sign a patient information and consent form to participate. The patient information and consent form will be approved by an appropriate ethics committee.

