## 8. STUDY DESIGN

### 8.1. Study Design

This study is a single-arm, evaluator masked clinical evaluation study of refractive stability, after successful bilateral cataract surgery. Subjects will be assessed pre-operatively, operatively and at 1 month and 3 months post-operatively. Clinical evaluations will include measurement of bilateral visual acuity, manifest refraction, and defocus curve.

The primary outcome measure will be the refractive stability (spherical equivalent change  $\leq 0.50D$ ) from 1-month to 3-months.

Secondary outcome measures are as follows:

- Binocular visual acuity outcomes (uncorrected and best-distance-corrected) at distance (4-6 m) and intermediate (80 cm) at 1 month and 3 months
- Percentage of patients cumulative distribution achieving 20/20 or better, 20/25 or better, 20/30 or better and 20/40 or better intermediate vision at 80 cm

- Binocular defocus curve at 3 months

Exploratory outcome measures are as follows:

- Binocular intermediate VA (66 cm) at 3 months

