### **10. ANALYSIS PLAN**

#### ***10.1. Analysis Data Sets***

All subjects who are enrolled in the study will be evaluated for safety. Efficacy analyses will be performed based on data from those eyes where uncomplicated cataract surgery with Clareon IOL implantation was completed.

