### ***10.3. General Statistical Considerations***

The statistical analyses will be performed using R, version 4.0.3 or higher. Any statistical tests of hypotheses will employ a level of significance of  $\alpha=0.05$ .

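### The primary hypothesis concerns the share of subjects stable within 0.50 D, but the only planned inference is a TOST on mean change with no margin

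*Combined protocol and SAP*

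**What the plan says.** - **Hypothesis.** Section 3 expects the lens to give "stable refractive stability evaluated over the postoperative 3 months with 80% of subjects achieving" a spherical equivalent change of 0.50 D or less from 1 to 3 months. Section 8.1 makes that threshold and window primary ("The primary outcome measure will be the refractive stability"). The 80% figure appears only in section 3.
- **Description.** Section 10.2 says that for categorical variables "summaries will provide the number and percentage of subjects who provided each score (or change in scores"), and then that "These summaries will be provided for all eyes completing the study".
- **Inference.** Section 10.2.1: "For variables measured on a continuous scale, the statistical significance of within-treatment changes between time points will be investigated using the TOST equivalence test". No equivalence margin is given. Section 10.3 sets alpha at 0.05 for any test that is done.
- **Unit.** Section 7.1: "Both eyes of a subject must be enrolled". Section 10.1: "Efficacy analyses will be performed based on data from those eyes where uncomplicated cataract surgery with Clareon IOL implantation was completed". Section 3 counts subjects in the hypothesis.
- **Power.** Section 11 asks for at least 23 patients (46 eyes), for 90% power at two-sided 5%, to detect a mean paired difference of 0.50 D with an SD of differences of 0.5. It enrols 30 patients (60 eyes).

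**The concern.** The hypothesis is about the spread of individual changes: how many subjects stay within 0.50 D. The inference and the power are about the centre of those changes. A mean near zero is compatible with many subjects moving by more than 0.50 D in either direction, so the two questions can have different answers.

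Three elements are missing: an interval or decision rule for the proportion, a margin for the TOST, and a rule that makes one subject result from two eyes (including when only one eye qualifies). A TOST pass could then be reported as proof of stability, or a bare 80% as confirmation of the hypothesis, when neither shows it. The choice between eyes and subjects could also be made after the results are known.

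**Working it through.** **1. The plan's own sample size.** Inputs from section 11: difference 0.50, SD of differences 0.5, two-sided 5%, power 90%. The paired normal formula gives ((1.960 + 1.282) × 0.5/0.5)² = 10.5, so 11 pairs; the paired t-test gives 13. The stated 23 does not follow from these inputs. It matches the per-group size of an independent two-sample t-test (22.02, rounded up to 23 per group, 46 in total). The paired t-test has power 0.996 with 23 subjects, so power for the mean is not short. On no reading does the figure concern a proportion.

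**2. Can the TOST pass when the hypothesis is false?** Assume normal change with mean 0, one value per subject and n = 30. The proportion stable is P(|X| ≤ 0.50) = 2Φ(0.50/SD) − 1. The TOST is t-based at 5% per side. Margins of 0.25 and 0.50 D are assumptions, since none is stated. Rounding of spherical equivalent to 0.125 D steps, which moves the effective limit to 0.5625 D, is also an assumption.

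| SD (D) | Within 0.50 D | Same, rounded | TOST passes, 0.25 D | TOST passes, 0.50 D |
|---|---|---|---|---|
| 0.30 | 90% | 94% | 99.5% | 100% |
| 0.39 | 80% | 85% | 93% | 100% |
| 0.44 | 74% | 80% | 84% | 100% |
| 0.50 (section 11) | 68% | 74% | 70% | 99.98% |

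The largest SD compatible with 80% is 0.50/1.2816 = 0.39 D, or 0.5625/1.2816 = 0.44 D with rounding. The planning SD exceeds both.

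**3. Can it fail when the hypothesis is true?** With mean 0.20 D and SD 0.25 D, P(|X| ≤ 0.50) = Φ(1.2) − Φ(−2.8) = 0.88. The TOST passes 28% of the time with a 0.25 D margin and 100% with 0.50 D.

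**4. Does the two-eye rule matter?** Assume bivariate normal changes with a between-eye correlation of 0.3 to 0.7. The mean of two eyes has SD × √((1 + ρ)/2).

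| SD per eye (D) | Both eyes stable | Mean of eyes stable |
|---|---|---|
| 0.30 | 82–85% | 93–96% |
| 0.39 | 65–69% (73–77% rounded) | 84–89% (86–91% rounded) |
| 0.50 | 48–53% (56–61% rounded) | 72–79% (75–81% rounded) |

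Unrounded, the two definitions fall on opposite sides of 80% for SDs of about 0.33 to 0.42 D across this range of correlations.

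**5. How precise is the percentage?** The exact (Clopper-Pearson) 95% interval for 24/30 is 61.4% to 92.3%. If an observed 24/30 or more were read as success, that would happen with probability 0.16 at a true 70% and 0.35 at a true 75%.

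**The case against.** The strongest reply is that the 80% is a descriptive expectation. It appears once, in the synopsis, while sections 6 and 8.1 speak only of evaluating stability in a small single-arm study. On that reading a missing interval is a reporting weakness, and no decision rule is needed. This has weight, and it is why estimation rather than a mandatory test is proposed. But section 3 calls the statement the hypothesis, and the one inferential method offered still answers a different question.

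A second reply is that 0.50 D is the natural margin. No section says so. If it were adopted, the failure in step 3 would disappear: under normality, 80% within 0.50 D puts the mean at least about 0.84 SD inside the limit, whereas the TOST with n = 30 needs only about 1.699/√30 = 0.31 SD. The mismatch would then run one way, with the TOST passing when fewer than 80% are stable. That is the more serious direction.

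Third, sections 10.1 and 10.2 can be read as an eye-level analysis, which would settle the subject with one qualifying eye. It would still conflict with the subject-level hypothesis and leave pairing unaddressed. At SD 0.39 D and correlations of 0.3, 0.5 and 0.7, 60 eyes are worth about 57, 52 and 45 independent eyes. It is fair to add that the two-eye rules in step 4 are illustrations not found in the protocol, and that at SD 0.50 D the definitions straddle 80% only with rounding and a low correlation.

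**Conclusion.** The concern holds, and it should be corrected before analysis. The analysis does not match the primary hypothesis; this is more than missing detail. At the plan's own SD of 0.5 D and zero mean change, about 68% of changes are within 0.50 D (74% rounded), short of 80%, yet a TOST with a 0.50 D margin would almost always succeed. The percentage alone is imprecise: 24/30 is compatible with 61% to 92%.

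These figures rest on normal changes, one value per subject in the TOST comparison, assumed margins and an assumed between-eye correlation. They illustrate what could happen and do not predict this lens's results. If the true SD is near 0.30 D with zero mean, every reading examined exceeds 80% and the TOST agrees. The mismatch itself depends on none of these assumptions, because a test of a mean is not a test of a proportion.

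**What to change.** In sections 10.2 and 10.2.1:

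1. Make the primary analysis the number and percentage of evaluable subjects whose absolute spherical equivalent change (3 months minus 1 month) is 0.50 D or less, with an exact (Clopper-Pearson) 95% interval.
2. Define evaluable before analysis, for example an eye that meets section 10.1 and has manifest refractions at both visits, and say how a subject with only one such eye is handled. Fix whether a stable subject means both eyes, one preselected eye, or the mean of the two. Requiring both eyes is the strictest of these and need not be the default. If eyes are the unit, use an interval that accounts for pairing.
3. Label the TOST on mean change as supportive and state its margin in advance.
4. State that the study estimates the proportion and that an observed 80% alone does not demonstrate the hypothesis. If a formal test against 80% is wanted, give its null, alpha and sidedness.

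In section 11, say that the 90% power refers to a mean difference of 0.50 D and not to the 80% hypothesis. Add the expected width of the 95% interval: with 30 subjects, about 30 points at a true 80% and 24 at 90%; with 23 subjects, 34 and 27.

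The cost is wording and a few lines of R, with no new data, visits or enrolment. The stated uncertainty will look less favourable. The optional test is weak. At one-sided 5% with 30 subjects it needs 28/30 (size 0.044), with power 0.41 at a true 90% and 0.81 at 95%. With 23 subjects it needs 22/23, with power 0.32 and 0.68. That is the reason to make estimation primary.

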### ***10.3. General Statistical Considerations***

The statistical analyses will be performed using R, version 4.0.3 or higher. Any statistical tests of hypotheses will employ a level of significance of  $\alpha=0.05$ .

## **11. SAMPLE SIZE JUSTIFICATION**

We estimate that the study would require a sample size of at least 23 patients (46 eyes) to achieve a power of 90% and a level of significance of 5% (two sided), for detecting a mean of the differences of 0.50D between pairs, and assuming the standard deviation of the differences to be 0.5. For additional power of the study and for any possible patients that leave the study prematurely, we are recommending a total of 30 patients (60 eyes)

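### Section 11's minimum of 23 patients for 90% power does not follow from its own inputs, which require 13 pairs; for the stated paired test the error is on the safe side

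*Combined protocol and SAP*

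**What the plan says.** Section 11 asks for "at least 23 patients (46 eyes) to achieve a power of 90% and a level of significance of 5% (two sided"). The target is given as "for detecting a mean of the differences of 0.50D between pairs, and assuming the standard deviation of the differences to be 0.5". The number is then raised to 30 patients (60 eyes) to add power and to cover early withdrawals. No withdrawal rate, test or formula is given.

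Three other places bear on how this should be read:

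- Section 3 (General Information) describes a "Prospective, non-randomized, single-arm study" and lists no control article.
- Section 3 also states the hypothesis as refractive stability "evaluated over the postoperative 3 months with 80% of subjects achieving" a spherical equivalent change of at most 0.50 D between 1 and 3 months.
- Section 10.2.1 says that, for continuous variables, "within-treatment changes between time points will be investigated using the TOST equivalence test". No equivalence margin is given there.

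**The concern.** Section 11 supplies everything a paired calculation needs: the mean difference, the SD of the differences, the significance level, its sidedness and the power. The answer is therefore fixed once the test is chosen, and it should come out near 23. A mean difference equal to one SD of the differences is a large effect, and 23 pairs looks too many for it.

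If 23 cannot be recovered, at least one of the test, the SD and the unit of analysis (patient or eye) has been misreported. Which one matters, because the power at 30 patients depends on the answer. The statement is also what a journal reader or ethics committee would use to judge whether the study is the right size.

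**Working it through.** **Inputs, all from section 11.** Mean paired difference δ = 0.50 D; SD of the differences σ = 0.5; two-sided α = 0.05; power 0.90. Standardised effect d = δ/σ = 0.50/0.5 = 1.0.

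**Attempt to reproduce 23 with a paired test.**

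Normal approximation: n = (1.960 + 1.282)² × (0.5/0.5)² = 10.51, so 11 pairs.

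Exact paired t-test: power is the probability that a noncentral t variable with n − 1 degrees of freedom and noncentrality d√n falls beyond ± the 97.5% point of the central t.

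| Pairs | Power |
|---|---|
| 12 | 88.3% |
| 13 | 91.1% |
| 23 | 99.6% |
| 30 | 99.96% |
| 46 | over 99.99% |

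The requirement is 13 pairs. The stated minimum exceeds it by 23 − 13 = 10, and 10/13 = 77%.

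**Other readings.**

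- *Eyes as the pairs:* 46 pairs give over 99.99%. If the two eyes of a patient were perfectly correlated, the effective number would fall to 23, still 99.6%.
- *Withdrawals:* the allowance is added after the 23, to reach 30, so it cannot explain the 23.
- *One-sided test:* 11 pairs exact, 9 by the normal approximation.
- *Wilcoxon signed-rank:* dividing 13 by a relative efficiency of 0.955 or 0.864 gives 13.6 or 15.05, so 14 to 16 pairs.
- *TOST:* assuming a margin of 0.50 D and no true change (neither is stated for this purpose), 13 pairs at 5% per side and 16 at 2.5% per side.

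None gives 23.

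**Readings that come close but contradict the text.**

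- *Two independent samples, d = 1.0.* The noncentrality is d√(n/2) with 2n − 2 degrees of freedom. Power is 89.97% at 22 per group and 91.2% at 23 per group. The requirement is 23 per group, 46 in total, the same pair of numbers as in section 11. The design has no second group, however, and section 11 specifies pairs. The match suggests an origin but does not prove one.
- *0.5 D taken as the SD at each visit.* Then the SD of the differences is 0.5 × √(2(1 − ρ)), where ρ is the correlation between visits. The documents do not give ρ. At ρ = 0, 0.25 and 0.5 the requirement is 24, 18 and 13 pairs. The extreme case, ρ = 0, gives an SD of about 0.71 D. With 0.71 D, power is 89.7% at 23 pairs, 91.0% at 24 and 96.1% at 30.

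**Working backwards.** With 23 pairs, 90% power is reached for a mean difference of about 0.354 D at an SD of 0.5, or for an SD of up to about 0.707 D at a mean difference of 0.50 D. Neither is what section 11 states.

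**The case against.** The strongest reply is that nothing turns on this. Section 11 sets a floor, 23 pairs do exceed 90% power, and the study plans 30. No decision about enrolment, visits or data would change. That stands, and it limits the weight of the point. It does not make the statement correct: a required size 77% above what its own inputs give is not a rounding difference.

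A second reply is that the error is on the safe side only if the stated SD and the paired test are both right. If the SD of the differences was meant to be about 0.71 D, 23 pairs fall just short of 90% and 24 are needed. This also stands, so the reassurance must be tied to the stated paired test. The 0.71 D figure is itself an assumption, and zero correlation between refractions of the same eye two months apart is an extreme case.

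A third reply is that adequacy for detecting a mean shift says little about the planned analyses. That is true. With SD 0.5 and no true change, 30 patients give over 99.9% TOST power at an assumed margin of 0.50 D, but about 70% at an assumed margin of 0.25 D, where 45 would be needed for 90%. Nor does the calculation address the proportion of subjects within 0.50 D. This is a reason to state the limits of the corrected figure, not to leave section 11 as it is.

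**Conclusion.** The concern holds. Section 11's inputs require 13 pairs, not 23, and the power at its stated minimum is 99.6%, not 90%. This rests only on figures printed in section 11 and on a paired t-test; the alternative paired readings tried give between 9 and 16.

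For that test, 30 patients are more than enough (99.96%), and they would still give about 96% if the SD of the differences were 0.71 D. The practical impact is therefore low, but the statement should be corrected because it cannot be reproduced and leaves the test, SD and unit unclear. The finding makes no claim about power for the TOST or for the 80%-of-subjects hypothesis.

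**What to change.** Restate section 11 so that n, power, SD and test agree, and name the test and the unit of analysis (patient or eye). This error gives no reason to change the planned 30 patients. The sponsor should confirm which SD was intended and use the matching text.

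If the SD of the differences is 0.5 D:

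> Thirteen pairs give 91% power to detect a mean shift of 0.50 D (paired t-test, two-sided 5%); 23 give 99.6% and 30 give over 99.9%.

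If it was meant to be about 0.71 D, state that SD and its basis, a required size of 24 pairs (91% power), and about 96% power at 30.

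In either case add:

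> This power applies to detecting a mean shift. It does not apply to the TOST analysis in section 10.2.1 or to the 80%-of-subjects hypothesis in section 3.

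The cost is two or three sentences in section 11, with no change to enrolment, visits or data collection.

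### Section 11 sizes the trial with difference-test inputs, but the planned test is TOST equivalence, so the stated 90% power does not belong to the planned analysis

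*Combined protocol and SAP*

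**What the plan says.** Section 11 sets a minimum of 23 patients, or 46 eyes, for 90% power. The test behind that figure is given as "a level of significance of 5% (two sided), for detecting a mean of the differences of 0.50D between pairs". The SD of the paired differences is put at 0.5. The section then rounds up to 30 patients (60 eyes) for extra power and early withdrawals, without giving a dropout rate.

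Section 10.2.1 says that for continuous variables "the statistical significance of within-treatment changes between time points will be investigated using the TOST equivalence test". No other inferential test is named in the plan. It gives no equivalence margin.

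Section 10.3 adds: "Any statistical tests of hypotheses will employ a level of significance of" 0.05. It does not say whether this applies to each one-sided test or overall.

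Three further places bear on the point. Section 3 states the hypothesis as a proportion: 80% of subjects change by 0.50 D or less between 1 and 3 months. Section 10.1 defines the efficacy data by eye, and Section 10.2 summarises all eyes that complete the study.

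**The concern.** A difference test and an equivalence test answer opposite questions.

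- **Section 11 as worded:** the null is a mean change of zero, the alternative is a mean change of 0.50 D, and alpha is two-sided 5%. Success means rejecting zero.
- **TOST (Section 10.2.1):** the null is a mean change at least as large as a margin, and the alternative is a change inside it. There are two one-sided tests. Success means a mean change close to zero.

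The trial's aim is to show stability, which is the TOST direction. A reader will take 90% as the chance of reaching that conclusion. Nothing in Section 11 supports this, because power for TOST depends on a margin and an assumed true mean change, and the plan gives neither. If 0.50 D were the margin, the change that Section 11 plans for would sit exactly on the TOST null boundary.

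The two alpha statements also leave it unclear whether a 90% or a 95% interval decides. A margin chosen after the data are seen could decide the equivalence result.

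**Working it through.** **Inputs from the documents.** Alpha 0.05 two-sided, power 0.90, mean of differences 0.50, SD of differences 0.5 (unit taken as D), n = 23 or 30 (all Section 11); test = TOST (Section 10.2.1); alpha 0.05 (Section 10.3).

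**Assumptions.** One value per subject; 5% for each one-sided test; the TOST margin M and the true mean change μ as shown below.

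**Step 1: the plan's own figure, as worded.** Paired formula:

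n = [SD × (z₀.₉₇₅ + z₀.₉₀) / δ]² = [0.5 × (1.960 + 1.282) / 0.5]² ≈ 10.5, so 11.

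The exact noncentral-t calculation gives 13 (power 91.1%). At n = 23 the noncentrality is (0.5/0.5) × √23 = 4.80 and the power is 99.6%. The 23 at 90% is not reproduced.

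**Step 2: where 23 can come from.** Two formulas for independent groups give 23 per group, 46 in total:

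- two-group difference t-test, two-sided 5%: 91.2% at 23 per group (89.97% at 22);
- two-group TOST, margin 0.50 D, true difference 0, 5% per side: 91.0% at 23 per group (89.4% at 22).

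Neither fits a single-arm design with paired visits, and the number cannot show which was run.

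**Step 3: power of the planned test.** Paired TOST concludes equivalence when |mean change| + t₀.₉₅,ₙ₋₁ × s/√n < M, that is, when the 90% interval lies inside ±M. Power is the probability of that event, integrated over the sampling distribution of s, with true SD 0.5 D.

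| Margin M (assumed) | True mean change μ (assumed) | n = 23 | n = 30 | n for 90% |
|---|---|---|---|---|
| 0.50 D | 0 | 99.7% | 99.98% | 13 |
| 0.50 D | 0.10 D | 98.1% | 99.6% | 15 |
| 0.50 D | 0.25 D | 75.1% | 84.8% | 36 |
| 0.25 D (illustration only) | 0 | 50.3% | 69.7% | 45 |

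**Step 4: the interval question.** At n = 23, M = 0.50 D and an observed SD of 0.5 D, the largest mean change that passes is:

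- 90% interval: 0.50 − 1.717 × 0.5/√23 = 0.321 D;
- 95% interval: 0.50 − 2.074 × 0.5/√23 = 0.284 D.

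At 2.5% per side (95% interval) and M = 0.50 D, power at μ = 0 is 99.1% (n = 23) and 99.9% (n = 30). At μ = 0.25 D it is 63.0% and 75.4%.

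**The case against.** **The 0.50 D may be a loosely worded margin.** A two-group TOST with that margin also returns 23 per group, so the author may have had equivalence in mind. This stands as far as it goes: the number does not reveal which test was sized. The point therefore rests on the wording of Section 11, which speaks of detecting a mean difference at a two-sided level. If TOST was meant, that wording misdescribes it, the two-group formula does not fit this design, and the same correction is needed.

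**The trial is large enough anyway.** On the only refractive-change threshold in the documents, 0.50 D, this stands for a true mean change near zero. It limits the harm to a wrong power statement but does not make that statement right.

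**The interval ambiguity is minor.** The natural reading of Section 10.3 is 5% per one-sided test, hence a 90% interval, and 0.32 D versus 0.28 D is a small gap. That is fair; it costs one phrase to settle.

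**Stronger readings that the documents do not support.** A reader might infer that the 90% is the chance of detecting a 0.50 D drift, or of finding the lens unstable. It is not: on the stated paired inputs that chance is 99.6% at 23 patients. Rejecting a zero mean change is also not the same as breaching the protocol's stability limit, which applies to individual changes. A reader might also quote 5% as the low end of the trial's power, since TOST with a 0.50 D margin passes 5% of the time at a true change of 0.50 D. That 5% is the type I error at the null boundary. It is the same at every sample size and is not power under any planning alternative.

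**Conclusion.** The point holds as a mismatch between Sections 11 and 10.2.1. The stated 90% is not the power of the planned TOST, and it does not match the paired difference test that Section 11 describes (99.6% at 23 patients; 13 patients give 91%).

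It does not follow that the trial is too small. With 0.50 D as the margin, SD 0.5 D, one value per subject and 5% per side, power at a true change of zero is 99.7% with 23 subjects and above 99.9% with 30, so the planned size is adequate for this test. If the true change were 0.25 D, power would be 75% and 85%, and 36 subjects would be needed for 90%. A shortfall at zero true change appears only with a much tighter margin. The 0.25 D case (50% and 70%) illustrates this, but that margin appears nowhere in the documents.

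None of these figures is power for the 80%-of-subjects hypothesis in Section 3. TOST is planned for continuous variables, and no test is assigned to that proportion. The correction should be made, but it does not change the number of patients.

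**What to change.** Keep 30 subjects and make these changes.

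1. **Section 11:** delete "for detecting a mean of the differences of 0.50D between pairs" and the two-sided 5%. Restate the justification for TOST: 5% for each one-sided test (90% interval inside the margin), SD 0.5 D, a stated margin, a stated assumed true mean change, and the resulting power. Possible text if 0.50 D is adopted: *With 30 subjects, one value per subject, an SD of 0.5 D and an equivalence margin of ±0.50 D, two one-sided tests at 5% each have above 99.9% power if the true mean change is 0 and 85% if it is 0.25 D.* Also give the figures for 23 subjects (99.7% and 75%) if that remains the minimum.
2. **Section 10.2.1:** state the same margin and the same interval.
3. **Unit of analysis:** use one value per subject, or analyse eyes with the correlation between fellow eyes handled. Reconcile the choice with the eye-level wording of Sections 10.1 and 10.2.
4. **Scope:** say in Section 11 that this power is for the mean-change TOST and not for the 80%-of-subjects hypothesis in Section 3.

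The cost is wording in Sections 10.2.1 and 11, with Sections 10.1 and 10.2 brought into line on the unit of analysis. No patients are added. The stated power may be less favourable if a margin tighter than 0.50 D is chosen.
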